5.1 Primary Endpoints

ICS and Azithromycin

The primary outcome targets admissions and death within 365 days of randomization. This is assessed in the following analysis:

- Number of hospitalization-requiring COPD exacerbations and/or death within 365 days (continuous data: analysis with chi squared test)

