2.1 Clinical objectives

ICS

- Whether a strategy of eosinophil-guided¹ administration of ICS in COPD patients with GOLD class E and/or FEV₁ < 30% can lead to non-inferior² treatment responses to triple therapy (ICS/LABA/LAMA).
- Whether side effects³ due to ICS exposure can be reduced with the eosinophil-guided administration of ICS.

Azithromycin

- Whether the use of prophylactic low dose Azithromycin⁴ in COPD patients with GOLD risk E and/or FEV₁ < 30% can reduce moderate and severe exacerbations.

¹ Blood eosinophils are measured every 3rd month during the study. If blood-eosinophils < 0.3 x 10⁹ cells/L, ICS treatment will be paused for the next 3 months. If blood-eosinophils are ≥ 0,3 x 10⁹ cells/L, ICS treatment will be continued/resumed during the next 3 months.

² Unchanged number of COPD exacerbations or death from all cause within 365 days

³ New diagnosis of diabetes mellitus, change in HbA1c and antibiotic requiring infections

⁴ 250 mg Azithromycin three times weekly

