2.2 Microbiota objectives

ICS

- Whether a strategy of eosinophil-guided administration of ICS in COPD patients with GOLD class E and/or $FEV_1 < 30\%$ leads to a change in (i) the respiratory microbiota abundance and diversity and (ii) the immunological profile in comparison to continuous triple therapy (ICS/LABA/LAMA).

Azithromycin

- Whether prophylactic low dose Azithromycin in COPD patients with GOLD class E and/or $FEV_1 < 30\%$ leads to changes in (i) the respiratory microbiota abundance and diversity and (ii) the immunological profile.

3. Hypotheses

ICS primary

- In COPD patients with GOLD class E and/or $FEV_1 < 30\%$, an eosinophil-guided administration of ICS treatment regimen is associated with no apparent loss of efficiency⁵.

ICS secondary

- In COPD patients with GOLD class E and/or $FEV_1 < 30\%$, eosinophil-guided administration of ICS will reduce the use of inhaled corticosteroids by $> 25\%$ ⁶.

⁵ Measured by "admissions with COPD exacerbation or death from all causes within 365 days

⁶ Measured by budesonide equivalent doses

- In COPD patients with GOLD class E and/or FEV₁ < 30%, eosinophil-guided administration of ICS will reduce the number of ICS related side effects.
- The respiratory microbiota have a composition of less "pathogenic" bacterial species in COPD patients with GOLD class E and/or FEV₁ < 30%, treated with the eosinophil-guided administration of ICS regimen compared to those treated with continuous triple therapy (ICS/LABA/LAMA) regimen.
- The complexity of the respiratory microbiota is lower among COPD patients with GOLD class E and/or FEV₁ < 30%, treated with continuous triple therapy (ICS/LABA/LAMA) regimen than among those treated with the eosinophil-guided administration of ICS regimen.
- The immunological profile of the upper airways changes in COPD patients with GOLD class E and/or FEV₁ < 30% treated with the eosinophil-guided ICS regimen compared to those treated with continuous triple therapy (ICS/LABA/LAMA) regimen.

Azithromycin primary

- In COPD patients with GOLD class E and/or FEV₁ < 30%, the use of low dose Azithromycin can result in a reduction in admissions with COPD exacerbation or death from all causes within 365 days" as compared to placebo.

Azithromycin secondary

- The difference in composition of the respiratory microbiota is substantial when COPD patients with GOLD class E and/or FEV₁ < 30% are treated with prophylactic low dose Azithromycin

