4.8 Research Biobank

The purpose of establishing a research biobank is to investigate the frequency of ICS-induced side effects and the changes in respiratory microbiota in different treatment groups. This biobank will clarify the hypotheses and provide biological materials for future research (Providing that future

projects can obtain a separate approval from the Danish National Committee on Health Research Ethics).

The research biobank will store blood samples, tracheal aspirate samples, and nasal swabs. Tracheal aspirate and nasal swab samples are taken from 40 participants from each treatment arm, in total 160 participants. Approximately 1-5 ml of tracheal aspirate will be collected from each participant. Blood samples are taken from each participant at inclusion and at follow-up every 3 months during the 12-month study period. Approximately 210 ml of blood will be collected during the entire study period corresponding to a maximum of 36 ml per blood draw. All samples are stored in a freezer at -80 degrees Celsius. The freezers are kept in a locked room at each of the participating pulmonary medicine departments.

All samples are pseudonymized and kept for 15 years in accordance with present legislation and data protection laws. Establishment of this research biobank ends **31AUG2027**. Following the end of this study and the research biobank, all surplus biological material will be transferred to a future-research biobank. These samples will also be pseudonymized and kept for 15 years. Permission to store biological material from participants in the research biobank and future-research biobank is a part of the informed consent to participation in the project.

5. Statistical Considerations (Power Calculation)

Participants will be randomized using stratified block randomization (REDCap) to ensure equal distribution of participants at the site, age (less than 70 years vs 70 years or more) and number of hospital-requiring exacerbations within the past 12 months (0-1 vs 2 or more).

The trial will have a target of 444 participants, , included in the project within 48 months, and 111 participants will be allocated to each of the four groups to be examined.

Two sample size calculations have been conducted, one for ICS and one for azithromycin, as there are two interventions being tested (factorial design):

A non-inferiority (1-sided) test for ICS.

Type 1 error limit (α) 2.5%, Power ($1-\beta$) of 80%. ($\alpha = 0.025$, $\beta = 0.2$)

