Control group exacerbation/death: 0.3 (30%)

Expected maximum worsening >11% absolute (up to 0.41)

Sample size 444 (222 x 2)

A 1-sided superiority test for azithromycin.

Type 1 error limit (α) 2.5%, Power ($1-\beta$) of 80%. ($\alpha = 0.025$, $\beta = 0.2$)

Control group exacerbation/death: 0.3 (30%)

Expected effect: >10% absolute (up to 0.2)

Sample size 444 (222 x 2)

These two interventions will be published separately in two primary publications, but there will be adjustments in the main analysis to account for whether they received the other intervention. These two analysis teams (separate) will be blinded to an effect estimate of the other intervention.

40 participants from each group will participate in the microbiota sub-study.

Scheduled analyses of data (Interim analysis) will be assessed when half of the participants are recruited. These assessments will be made by the independent Data and Safety Monitoring Board (DSMB) on the two primary endpoints, and for the secondary endpoint “Death or “uncontrolled AECOPD tendency” within 365 days”. Data on primary and secondary power targets will be used for this purpose. DSMB will review the protocol, monitor the guideline, evaluate the trial concerning the recruitment of participants, participants' risk and, based on interim analyses, make recommendations to the investigators on whether to continue or cease the study. DSMB may at any time require an extraordinary interim analysis

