As for Azithromycin, little is known about the mechanism of its effect. Only one large, randomized trial has been performed patients with severe COPD (50% had an exacerbation in the previous year) (22). We aim to determine how prophylactic long-term Azithromycin treatment alters airway inflammation and the respiratory microbiota, and whether Azithromycin can reduce exacerbation rates in COPD patients with GOLD class E and/or FEV₁ < 30%.

⁸ 20% of COPD patients in class C/D have blood eosinophil counts $\geq 0,3 \times 10^9$ cells/L.

We recognize the importance of understanding individual differences in clinical response, biological information, and microbiota changes in response to combined medication. We hope to provide an in-depth understanding of key biological and physiological mechanisms that lead to AECOPD with this study. With a better understanding of the interplay between microbiota changes and therapeutic influences on this by ICS and Azithromycin, the treatment of COPD symptoms can be continuously reevaluated and adapted to each patient.

11. Research Ethical Statement

The research project will be carried out in accordance with the Helsinki Declaration, the Danish Data Protection Act, the Danish Health Act, and the General Data Protection Regulation (EU) 2016/679 (GDPR).

The study is approved through the CTIS and will be conducted in compliance the Clinical Trials Regulation (EU) No 536/2014 (CTR) and with the principles of good clinical practice, as this statement a requirement under the CTR.

The study will be registered in the US Clinical Trials database (www.clinicaltrials.gov), which is based on guidelines defined by The Food and Drug Administration.

Since study participants will not be exposed to irresponsible risks and can greatly benefit from the study's results and participation in the study, we believe that the study is scientifically and ethically sound.

12. Informed Consent

Participation in the trial is voluntary, and participants will not receive any form of financial compensation for participation. . Participants are protected under the Personal Data Processing Act, and the study is reported to the Regional Science Ethics Committee (VEK), the Danish Medicines Agency (Lægemiddelstyrelsen), and the Danish Data Protection Agency (Videnscenter for Dataanmeldelser).

13. Compensation and Reimbursement Schemes

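### Section 5 plans the ICS question as a non-inferiority test with an 11-point limit, but Section 5.1 assigns it a chi-squared test of equality that never uses the limit

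*Protocol*

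**What the plan says.** Section 4.1 calls the trial a non-inferiority study. Section 5 (Statistical Considerations) names "A non-inferiority (1-sided) test for ICS", with a type 1 error of 2.5%, power of 80%, a control-group risk of 0.30, a maximum worsening of 11 points absolute (up to 0.41), and 444 participants (222 per side). The 11 points are not labelled a margin there. Section 5 also promises that each main analysis will be adjusted for the other intervention.

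Section 5.1, under a joint heading for ICS and azithromycin, gives a single analysis: "Number of hospitalization-requiring COPD exacerbations and/or death within 365 days (continuous data: analysis with chi squared test". The Data analysis section (the second of two numbered 5.3) lists t-tests, chi-squared, Fisher's exact and time-to-event methods for various outcomes, and sets none of them against a margin.

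Where the Protocol describes what non-inferior means, footnote 2 of Section 2.1 says "Unchanged number of COPD exacerbations or death from all cause within 365 days". The primary ICS hypothesis in Section 3 is that "an eosinophil-guided administration of ICS treatment regimen is associated with no apparent loss of efficiency". Neither refers to the 11 points.

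**The concern.** The test named for the primary ICS question has the wrong null hypothesis. Chi-squared takes equality as the null and can only reject it. A non-inferiority claim takes a worsening of at least 11 points as the null and must reject that. The two procedures can disagree on the same data, so the Protocol does not fix which one decides the ICS result.

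This is more than detail left to an SAP. Section 5.1 is not silent on the test: it names one, and that test conflicts with Section 5. An SAP that used the margin would depart from Section 5.1, and an SAP that followed Section 5.1 would contain no non-inferiority test. An unstratified chi-squared test also cannot deliver the adjustment that Section 5 promises. The line calls the data continuous and speaks of a number of events, whereas a planning risk of 0.30 and a chi-squared test both imply a yes/no outcome per participant.

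At stake is the primary ICS conclusion, namely whether ICS can be guided by eosinophil count without an unacceptable increase in admissions and deaths.

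**Working it through.** **Inputs (Section 5):** one-sided alpha 0.025, power 0.80, control risk 0.30, limit 0.11, 222 per side.

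**1. The plan's own sample size.** With both true risks at 0.30, n per side = 2 × 0.30 × 0.70 × (1.960 + 0.842)² / 0.11² = 0.42 × 7.849 / 0.0121 = 272.4. This rounds up to 273 per side, 546 in total. The stated 444 is not reproduced. A one-sided alpha of 0.05 would need 215 per side, and 222 would then give 81.2% power, but 0.05 is not the stated alpha.

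**2. Power of a margin-based rule at 222 per side.** The standard error is √(0.42/222) = 0.0435. Then 0.11/0.0435 − 1.960 = 0.569, and Φ(0.569) = 71.5%. Exact binomial enumeration gives 71.6%.

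**3. Chi-squared when the truth is exactly at the limit (0.30 v 0.41).**
- Pooled risk 0.355, so the null standard error is √(2 × 0.355 × 0.645/222) = 0.0454.
- The test is non-significant while the difference stays below 1.960 × 0.0454 = 0.0890.
- The true standard error is √((0.2100 + 0.2419)/222) = 0.0451.
- P(non-significant) ≈ Φ((0.0890 − 0.11)/0.0451) = Φ(−0.465) ≈ 32%. Exact enumeration gives 31.7%.

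**4. The two readings compared.** Exact enumeration, 222 per side, control 30%, two-sided 5% chi-squared without continuity correction, Wald 95% interval:

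| True risk, eosinophil-guided | Chi-squared non-significant | Upper 95% limit below +11 points |
|---|---|---|
| 30% | 94.9% | 71.6% |
| 35% | 79.7% | 27.1% |
| 41% (at the limit) | 31.7% | 2.4% |

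Only the last row is an error rate for a false non-inferiority claim: 31.7% against 2.4%, with 2.5% intended.

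**5. A single data set on which they disagree.** With 67/222 (30.2%) on control and 86/222 (38.7%) on the guided strategy, the difference is 19/222 = 8.6 points and chi-squared gives p = 0.058. The standard error is √((0.2107 + 0.2373)/222) = 0.0449, so the 95% interval is 8.6 ± 8.8, or −0.2 to +17.4 points. There is no significant difference, yet 11 points is far from excluded.

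**The case against.** The strongest reply is that the Protocol should be read as a whole. Section 5 states the test type, the alpha and the limit, and the interval method and decision wording commonly sit in an SAP that is not shown here. On that reading Section 5.1 is loose drafting, and the objective and hypothesis are plain-language statements. Part of this stands: the Protocol does plan a non-inferiority test, so the defect is a mismatch between two sections. It does not remove the mismatch, because Section 5.1 states a specific and different test for the same question.

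Three stronger readings are tempting and are not supported.

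- A reader might infer that the Protocol will treat a non-significant p-value as non-inferiority. No section says so. The 32% is therefore conditional on that reading.
- A reader might count trials with no true difference that are non-significant yet fail the margin (25.9% by enumeration) as false positives. With equal risks the strategy truly is non-inferior, so that figure reflects the limited power of the margin rule.
- A reader might argue that participants who stay on ICS in the guided arm dilute the comparison, using footnote 8 of Section 10 ("20% of COPD patients in class C/D have blood eosinophil counts" at or above the threshold), so that 11 points overall hides 0.11/0.80 = 13.75 points among those whose treatment changes. The objective is to test the strategy, and continuing ICS under it is part of the strategy. The 20% describes class C/D patients, whereas this trial also admits patients on FEV₁ alone and excludes some recent exacerbations. Treatment is also re-decided every three months. The documents do not support that calculation, nor a need for an eosinophil subgroup analysis on its account.

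**Conclusion.** The point holds as a contradiction in stated text. Section 5 plans a one-sided 2.5% non-inferiority test with an 11-point limit, and Section 5.1 assigns a test of equality that ignores the limit. Followed as written, the analysis in Section 5.1 cannot support the primary ICS conclusion. For azithromycin a test of difference suits the superiority question, apart from the missing adjustment and the data label.

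If non-significance were read as non-inferiority, the chance of accepting a strategy 11 points worse would be about 32%, against 2.4% under a margin-based rule. This rests on a binary endpoint, 222 analysed per side, a 30% control risk, a two-sided 5% chi-squared test, and unadjusted binomial comparisons with no allowance for dropout. Applying the margin-based rule also exposes a power of about 72% at 444 participants, against the stated 80%. This should be corrected before any unblinded analysis.

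**What to change.** 1. In Section 5.1, define the primary endpoint as binary: at least one COPD exacerbation needing admission, or death from any cause, within 365 days of randomization. Remove the label continuous.
2. Split the analysis. For ICS, state 11 percentage points as the margin on the risk difference (eosinophil-guided minus control), estimate that difference adjusted for azithromycin allocation, and conclude non-inferiority only if the upper limit of the two-sided 95% confidence interval is below +11 points.
3. For azithromycin, keep a superiority test, adjusted for ICS allocation.
4. Align footnote 2 of Section 2.1 and the primary ICS hypothesis in Section 3 with this rule.
5. Restate the ICS power in Section 5: about 72% with 222 per side and 30% in both groups. Reaching 80% would take about 273 per side, or 546 − 444 = 102 more participants.

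Items 1 to 4 cost wording only and need no new data. Item 5 is the real cost: the sponsor must either accept and disclose the lower power or enlarge the trial.

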5.3 Data analysis

The four treatment groups will be compared in terms of endpoints at inclusion and follow-up visits every 3 months from trial inclusion with standard statistical tests such as t-test (Dichotomous outcomes), chi-squared test, Fisher's exact test, and time-to-event analyses.

Recurrence of AECOPD, the period between index AECOPD and the next AECOPD, and number of admission-requiring NIV treatment within 365 days are analyzed using Fisher's exact test or Chi-

squared test. Time to AECOPD within 365 days and number of hospitalization-requiring exacerbations within 365 days will be analyzed with t-test and Cox proportional-hazards regression model (unadjusted and adjusted). Mortality rate within 365 days will be analyzed with Chi-squared test or Fisher's exact test (unadjusted) and with Cox proportional-hazards regression model (adjusted).

New onset of diabetes during the study period or occurrence of antibiotic-requiring infections within 365 days will be analyzed using Fisher's exact test or Chi-squared test. Changes in lung function, health-related quality-of-life (CAT), and level of dyspnea (MRC) will be analyzed using analysis of variance (ANOVA). The cumulative ICS dose will be analyzed as mean total cumulative dose from recruitment to end of the study period using t-test, Wilcoxon signed-rank test or Mann-Whitney U test.

6. Risks and Side Effects

Possible side effects from the use of ICS (Beclometasondipropionat) according to pro.medicin.dk are:

Common (1-10%): Pharyngitis, Coughing, Hoarseness, Headache, Candidiasis.

Uncommon (0.1-1%): Blurry vision, Dizziness, Tremor.

Rare (0.01-0.1%): Allergic reactions, Angioedema, Bronchospasm.

Very rare (<0.01%): Adrenal insufficiency. Eosinophilic pneumonia. Erythema, purpura. Decrease in bone mineral density. Glaucoma, cataract. Growth retardation.

Unknown prevalence: Disturbed behavior, Aggressiveness, Anxiety, Depression, Hallucinations, Hyperactivity, Hypercorticism.

Possible side effects from the use of Azithromycin according to pro.medicin.dk are:

Very common (>10%): Abdominal pain, diarrhea, flatulence, nausea.

Common (1-10%): Tiredness or weakness. Decreased appetite. Vomiting, taste perversion. Decreased lymphocyte count. Decreased serum bicarbonate. Arthralgia. Headaches, Paresthesia, Dizziness. Skin itching, rash. Visual disturbances.

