Events will be considered exclusively within the trial period, encompassing participant enrollment from screening to the last visit day. An annual safety report (ASR) of all SARs and SUSARs occurring during the trial period along with a description of the rules of registration and reporting of adverse events as given in this protocol will be submitted to the Clinical Trials Information System (CTIS). All SAEs, SARs, SUSARs will be reported in the final report to the CTIS at the conclusion of the trial.

7. Exclusion from or interruption of the trial

Participants may at any time terminate the study if the physician responsible for the study deems it necessary with medical justification (allergy to the medicine, safety risk, or other adverse circumstances). The investigator can furthermore at all hours unblind the Azithromycin/placebo treatment by contacting Glostrup Apotek. Termination and unblinding should preferably be done in agreement with the coordinating investigator of the project. The participant in question will be informed immediately of health concerns, project termination, and future treatment plan. Additionally, participants may, at any time, withdraw their informed consent. This will not have any consequence on further treatment.

8. Economy

The initiative for the trial was taken by the steering committee of COP:TRIN (Chronic Obstructive Pulmonary Disease: Trial Network) and the departments of pulmonary medicine at Gentofte Hospital, Herlev Hospital, Hvidovre Hospital, Bispebjerg Hospital, North Zealand Hospital, and Aalborg Hospital. The project budget is approximately DKK 7.433.600. This amount will cover salary to researchers, supervisors, nurses and auxiliary staff, the cost of data collection, equipment, medication, laboratory analyses, diagnostic tests, and potential hospitalizations.

Funding has been sought from various foundations, including Region H Research Fund. The Scientific Ethics Committee and the trial participants will be informed of the sponsors, their financial contribution and its part in the project, and information on grant recipient (Whether the support is paid directly to the investigators or their department/institute).

The Novo Nordisk Foundation has supported the initiative with 4.6 million DKK by a grant to [name].

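### The chi-squared test named for the 365-day primary endpoint gives no limit to set against the 11-point ICS margin, cannot use partial follow-up, and does not fit the analyses named in sections 5 and 5.3

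*Protocol*

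**What the plan says.** Protocol section 5.1 defines the primary endpoint for both interventions in one line: "Number of hospitalization-requiring COPD exacerbations and/or death within 365 days (continuous data: analysis with chi squared test". The line calls the endpoint a number and continuous, yet the test named ("analysis with chi squared test") is one for categories.

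Section 5 (Statistical Considerations) plans "A non-inferiority (1-sided) test for ICS" with one-sided alpha 2.5% and 80% power. It assumes a control risk of 30% and a largest tolerated risk of 41%, with 222 participants per side. Azithromycin has a one-sided superiority test with 30% v 20% and the same number. The same section says that the main analysis of each intervention will be adjusted for receipt of the other. It names no model.

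5.3 Data analysis lists "chi-squared test, Fisher's exact test, and time-to-event analyses" among the standard methods. It names a t-test and Cox regression, unadjusted and adjusted, for time to AECOPD and for the number of hospitalised exacerbations, and adjusted Cox regression for mortality.

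On follow-up, section 7 states that "participants may, at any time, withdraw their informed consent". Section 4.2 lists hospital admissions among the items read from health files during the project, section 4.6 takes data from the electronic health record, and section 6 has the patient files checked every 3 months.

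**The concern.** There are three linked difficulties, all in what the protocol states.

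First, the ICS question is whether the risk difference can be shown to lie below 11 points. The usual chi-squared test asks whether the two risks are equal. Failing to reject equality does not show non-inferiority, and the test supplies no limit to set against the margin.

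Second, a 2x2 chi-squared test on day-365 status has no place for someone observed event-free to, say, day 200 and not afterwards. Unless that status is completed or imputed, the person is either dropped or counted as having no event. The two choices push the ICS result in opposite directions.

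Third, an unadjusted chi-squared test (5.1), an adjusted main analysis (5), and a t-test with Cox regression for the admissions component (5.3 Data analysis) cannot all be the primary analysis. Two separate teams will write the two main publications, so an unsettled primary analysis leaves room for different choices.

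**Working it through.** **Inputs from the protocol (section 5).** Control risk 0.30, limit 0.41, one-sided alpha 0.025, 222 per side.

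**The plan's own number.** With equal true risks, n per side = 2(0.30)(0.70)(1.960 + 0.842)² / 0.11² = 0.42 × 7.849 / 0.0121 = 272.4, so 273 per side and 546 in total, not 444. With 222 per side, SE = √(0.42/222) = 0.0435 and power = Φ(0.11/0.0435 − 1.96) = 72%. That is a separate matter; 222 is used below as stated.

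**Chi-squared against the margin.** With SE 0.0435, 1.96 × SE = 8.5 points. Chi-squared (two-sided 5%) is non-significant for any observed difference within ±8.5 points. Non-inferiority needs an observed difference below 11 − 8.5 = 2.5 points. Holding the SE fixed, an observed worsening between about 2.5 and 8.5 points is non-significant and yet does not show non-inferiority.

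**Partial follow-up: assumptions.** The protocol gives no loss rate, so every rate here is assumed. A leaver is someone whose outcome can no longer be observed. Event hazard λ and leaving hazard μ are constant over the year: λ = −ln(1 − risk), μ = −ln(1 − loss).
- Event seen before leaving: E = λ/(λ+μ) × [1 − e^−(λ+μ)]
- Left with no earlier event: L = μ/(λ+μ) × [1 − e^−(λ+μ)]
- Leavers scored event-free: the estimate is E. Leavers dropped: it is E/(1 − L).

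**At the margin (0.30 v 0.41), loss 5% control v 15% guided.**
- Control: λ = 0.3567, μ = 0.0513, E = 0.2929, L = 0.0421, E/(1 − L) = 0.3058.
- Guided: λ = 0.5276, μ = 0.1625, E = 0.3811, L = 0.1174, E/(1 − L) = 0.4318.
- Event-free: 38.1 − 29.3 = 8.8 points. Dropped: 43.2 − 30.6 = 12.6 points. Kaplan-Meier: 11.0 points.

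SE at the margin = √[(0.21 + 0.2419)/222] = 0.0451. A favourable shift of 2.18 points moves the one-sided error from 2.5% to Φ(−1.96 + 2.18/4.51) = 7.0%; simulation gave 6.7% to 6.9%. With leavers dropped, simulated error was 1.0% to 1.2%. With no true difference and the same loss, the simulated chance of showing non-inferiority was 57% with leavers dropped and 70% with Kaplan-Meier.

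**Other assumed losses (control v guided), leavers' risk unchanged after leaving.** Shift in points from the true difference; minus favours non-inferiority.

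| Loss | True 0: event-free | True 0: dropped | True 11: event-free | True 11: dropped |
|---|---|---|---|---|
| 5% v 5% | 0.0 | 0.0 | −0.2 | +0.1 |
| 20% v 20% | 0.0 | 0.0 | −1.0 | +0.4 |
| 5% v 10% | −0.7 | +0.6 | −1.2 | +0.8 |
| 5% v 15% | −1.5 | +1.3 | −2.2 | +1.6 |
| 5% v 20% | −2.2 | +2.0 | −3.2 | +2.4 |
| 15% v 5% | +1.5 | −1.3 | +1.2 | −1.2 |

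**Stress test of Kaplan-Meier.** Keep the true 365-day risks at 0.30 and 0.41 but let the hazard double after leaving. At 5% v 15% this needs λ = 0.3488 and 0.4946 before leaving. Kaplan-Meier then estimates (1 − e^−0.4946) − (1 − e^−0.3488) = 39.0 − 29.4 = 9.6 points, not 11.0. Dropping leavers gives 11.1. At 5% v 20% the figures are 8.9 and 11.3.

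**The case against.** A reader might infer that the chi-squared test forces every early leaver to be dropped or scored event-free, and that this moves the ICS result by 1 to 3 points. The documents do not support that. The endpoint is admission or death, not a visit measurement. Admissions are read from health files (4.2, 4.6), files are checked every 3 months (section 6), and the full 12-month follow-up can be done at home (4.5). Someone who stops treatment or misses visits can still have a day-365 status. Only those whose record access ends are at issue, and a proportion can also be analysed after imputation. With equal true risks of 30% and leavers scored event-free, a shift of 1 to 3 points needs loss to differ by about 7 to 20 points between arms (about 4 to 15 if leavers' hazard doubles). Nothing in the protocol gives such a gap. ICS switching does appear visible, since placebo is described only for azithromycin although the trial is called double blinded. That makes uneven withdrawal conceivable, but no more.

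It can also be said that missing-data rules belong in a SAP, which is not shown. That is right, and their absence is not the point. The point is that the protocol names a test that does not suit the stated non-inferiority question and conflicts with its own text elsewhere.

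The objection that Kaplan-Meier looks good only because loss was drawn independently of risk also stands in part: the stress test shows that it can be biased by more than dropping leavers. It limits what the fix can claim.

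**Conclusion.** The point holds in limited form. Section 5.1 fixes a test that provides no confidence limit for the 11-point comparison, mislabels the endpoint as continuous, and does not agree with section 5 or 5.3 Data analysis. These defects rest on the text alone.

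The part about partial follow-up is conditional. It concerns mainly participants who withdraw consent, and its size and sign are unknown. At a true 11-point worsening with 5% v 15% unobserved, the estimate is 8.8 or 12.6 points depending on the handling rule. With equal loss the shift is zero at no true difference, and at the margin it is at most about 1 point for losses up to 20%. These are illustrations under constant hazards and assumed loss rates, not predictions for this trial.

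**What to change.** Reconcile section 5, section 5.1 and 5.3 Data analysis on one primary estimate for both interventions: the difference in 365-day Kaplan-Meier risk of first hospitalised COPD exacerbation or death. Adjust it for the other intervention and for the randomisation factors (site, age group, prior hospitalised exacerbations). Compare its confidence limit with 11 points for ICS and with 0 for azithromycin. Remove the continuous-data label.

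Pool sparse site strata. The six departments named in section 8, by two age groups and two exacerbation groups, could give 24 strata, or about 222/24 ≈ 9 participants per side in each.

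State that day-365 status is completed from health files after treatment stops, and after withdrawal where consent allows. Keep the simple proportion as a sensitivity analysis, and add a scenario in which leavers have a higher later risk.

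The cost is wording in the protocol and SAP, plus confirming that the dates of admission, death and end of record access are held. With complete follow-up the unadjusted Kaplan-Meier difference equals the simple difference in proportions. The downside is that Kaplan-Meier assumes withdrawal is unrelated to later risk within each arm, which is why the added scenario is needed.
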